### 3. Abstract:

Proton Pump Inhibitors (PPIs) are indicated for the treatment of gastroesophageal reflux disease (GERD), *H. pylori* infection, peptic ulcer disease, and gastric protection in patients at risk for gastrointestinal bleeding. PPIs are among the most commonly prescribed drugs in the world, and their most common indication is GERD. Refractory GERD is the term used to describe non-responsiveness to conventional PPI therapy, and it occurs in up to 40% of patients even when the PPI dose is doubled. The efficacy of PPIs is highly dependent on plasma concentrations achieved following drug administration. All PPIs are metabolized in part by the *CYP2C19* enzyme, which is encoded by the highly polymorphic *CYP2C19* gene. Depending on the *CYP2C19* genotype, individuals are classified into different metabolizer phenotypes: poor metabolizers (PM, 2 loss-of-function *CYP2C19* alleles); intermediate metabolizers (IM, one loss-of-function allele); normal metabolizers (NM, no loss or gain-of-function alleles); rapid metabolizer (RM; one gain-of-function allele) and ultra-rapid metabolizers (UM, two gain-of function-alleles). Genetic variants in *CYP2C19* are known to profoundly influence PPI plasma concentrations and consequently, response to PPI therapy. For example, individuals classified as either RM or UM have lower PPI concentrations compared to NM, IMs, or PMs, respond poorly to PPI therapy, and some fail to respond even when the PPI dose is increased. **We hypothesize that genotype-supported treatment of GERD and dyspepsia will lead to better GERD control and improvement in severity of dyspepsia symptoms compared to conventional treatment.** We will conduct a comparative effectiveness study of genotype-supported vs. conventional treatment of GERD and dyspepsia. Patients presenting with GERD or dyspepsia symptoms and either 1) being initiated on PPI therapy or 2) with continued symptoms on current PPI therapy will be recruited from gastroenterology clinics and randomized to a genotype-supported versus conventional PPI therapy management strategy. We will integrate individual *CYP2C19* genotype information into treatment decisions for the genotype-supported arm and compare change in symptom control from baseline to the end of the study between study arms. Given that PPI efficacy is related to PPI exposure and to metabolizer phenotype, individualizing treatment using *CYP2C19* genotype information is expected to improve symptom

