Genotyping and result reporting. Genotyping will be done by the CLIA-licensed UF Pathology Laboratory, as has been done for over 1,600 patients in the UF Health CYP2C19-clopidogrel implementation, with genotype results reported in the EHR. For patients randomized to the genotype-supported arm, genotype results will be available in approximately 2 weeks. For patients randomized to the conventional treatment arm, the genotype results will be resulted in the EHR after the patient completes study participation (12 weeks after patient enrollment). The patient's clinician will be educated about the genotype results and their implication for PPI response. A recommendation for a dose increase will be provided for RMs and UMs (approximately 30% to 35% of patients). For patients with other genotypes, clinicians will be advised that usual PPI doses are expected to be effective that lower doses may be sufficient for symptoms management in PMs. Clinicians will also be provided quick reference guides that will include phenotype, genotype, dosing recommendations, and educational information. The PMP Committee has convened with the GI clinicians to evaluate and approve the dosing recommendations for adults based on CYP2C19 genotype. Clinical decision support tools in the EMR will also be implemented that will provide this guidance to the treating clinician. While dosing recommendations will be provided based on genotype results, the ultimate prescribing decision will be left to the discretion of the treating physician.

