**TABLE 1. CYP2C19 genotypes, inferred phenotypes, and population frequencies**

ALLELEx	GENOTYPE/ACTIVITY	PHENOTYPE b	FREQUENCY
*1/*1	Wild Type (WT) / 2 active alleles	NM	39%
*1/*n	Heterozygous WT/1 active, 1 LOF allele	IM	20%
*2/*2 or *n/*n	Homozygous variant/2 LOF alleles	PM	1.7%
*1/*17	Heterozygous WT/1 active, 1 GOF allele	RM	28%
*17/*17	Homozygous variant/2 GOF alleles	UM	5.3%
*2/*17	Heterozygous; 1 LOF/ 1 GOF allele	?	5.6%

a\*2, \*3, \*8, or \*9 refer to loss-of-function (LOF) alleles, n refers to any of the LOF alleles

bAbbreviations: GOF –gain of function; NM—normal metabolizer; IM – intermediate metabolizer; PM – poor metabolizer; RM—rapid metabolizer; UM—ultra-rapid metabolizer

[figure not shown]
Given that the frequencies of homozygous variants are relatively rare, our analyses will focus on three main phenotype groups from the five CYP2C19 phenotypes listed in **Table 1**. These will be those individuals carrying a LOF allele (hereafter referred to as PMs), those with no variant alleles (hereafter referred to as NMs) and those carrying a gain of function allele (hereafter referred to as RMs). As noted, those who are \*2/\*17 will not be included in the primary analysis since the relevant phenotype is not clear. In secondary analyses we will associate outcomes with the five phenotypes listed in table 1.

***Efficacy of PPIs depends on plasma concentrations and CYP2C19 genetic variation.*** Studies in adults and children report that the efficacy of PPIs to treat GERD and related conditions are closely linked to plasma concentrations . Numerous studies in adults have shown that CYP2C19 variants markedly influence the pharmacokinetics and pharmacodynamics of PPIs (see reviews 6,16-18,23,31-33). H pylori cure rates are significantly higher among PMs compared to RMs  and higher doses of PPI are required to treat H pylori in RMs. There are fewer studies in children. Although earlier studies suggested that CYP2C19 variants had little effects on PPI PK in children, recent studies support a role for CYP2C19 variants.

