#### **STUDY DESIGN\_ Focus on Aim2 for Nemours Children's Hospital**

**Aim 2: Implement pharmacogenetic testing of the CYP2C19 gene-PPI drug pair in adults at UF Health and in children at Nemours Children's Hospital in the context of a comparative effectiveness genotype-supported vs. conventional PPI dosing trial.**

Overview. We have designed a comparative effectiveness clinical trial testing conventional PPI dosing with genotype-supported dosing with clinically meaningful outcomes to determine the feasibility of genetic testing in a pediatric and adult setting. The primary outcome is a composite end point of upper respiratory infections pneumonia, acute gastroenteritis, adverse kidney effects and bone fractures.

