**Dosing.** All participants will be genotyped and those randomized to the conventional arm will be dosed according to FDA product labeling. At Nemours, for those randomized to genotype-supported arm, the treating clinician will be provided dosing recommendations with the dosing recommendations based on CYP2C19 genotype-inferred metabolizer phenotype. Specifically, for participants classified as PM and IM we will recommend that their conventional (based on NM phenotype) PPI doses be reduced 50% (halved). We will recommend that conventional PPI doses be increased 50% and 100% for RMs and UMs, respectively. For participants with the \*2/\*17 diplotypes we recommend they be dosed as NMs. At UF Health, the PMP Committee will convene with the GI clinicians to evaluate and approve and or modify the recommendations for adults. Treatment will be 8-12 weeks. At NCH, clinical support in regards to PPI recommended dosing per CYP2C19 metabolizer phenotype will be provided to GI physicians in EPIC (EMR system). High PPI doses will be aligned with current clinical practices by doubling the original dose..

**Table 5.** PPI dosing guide per metabolizer phenotype

Metabolizer Phenotype	PPI recommended dosing
NM or Inconclusive (Conventional dosing)	Esomeprazole (Nexium) <10 kg: 5 mg daily; 10-20 kg: 10 mg daily; > 20 kg: 20 mg daily Lansoprazole (Prevacid) <15kg: 7.5mg daily; 15-30 kg: 15 mg daily; > 30 kg: 30 mg daily Omeprazole (Prilosec) <10 kg: 5 mg daily; 10-20 kg: 10 mg daily; > 20 kg: 20 mg daily Pantoprazole (Protonix) <10 kg: 5 mg daily; 10-20 kg: 10 mg daily; > 20 kg: 20 mg daily
PM or IM (50%↓ of Conventional dosing)	Esomeprazole (Nexium) <10 kg: 2.5 mg daily; 10-20 kg: 5 mg daily; > 20 kg: 10 mg daily Lansoprazole (Prevacid) <15kg: 3.75mg daily; 15-30 kg: 7.5mg daily; > 30 kg: 15mg daily Omeprazole (Prilosec) <10 kg: 2.5 mg daily; 10-20 kg: 5 mg daily; > 20 kg: 10 mg daily Pantoprazole (Protonix) <10 kg: 2.5 mg daily; 10-20 kg: 5 mg daily; > 20 kg: 10 mg daily
RM (50% ↑ of Conventional dosing)	Esomeprazole (Nexium) <10 kg: 7.5mg daily; 10-20 kg: 15 mg daily; > 20 kg: 30 mg daily Lansoprazole (Prevacid) <15kg: 11.25mg daily; 15-30 kg: 22.5mg daily; > 30 kg: 45mg daily Omeprazole (Prilosec) <10 kg: 7.5 mg daily; 10-20 kg: 15 mg daily; > 20 kg: 30 mg daily Pantoprazole (Protonix) <10 kg: 7.5 mg daily; 10-20 kg: 15 mg daily; > 20 kg: 30 mg daily

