Statistical analysis. We will have two primary hypotheses tested in this pragmatic clinical trial: 1. Hypothesis: RMs (1 or 2 GOF alleles) in the genotype-supported arm have better GERD control than RMs in the usual care group 2. Hypothesis: PMs (1 or 2 LOF alleles) in the genotype-supported group have fewer adverse effects (composite of URI/GI infections, kidney adverse effects, bone fracture) than PMs in the usual care group. Continuous variables will be compared between the genotype-supported group and the usual care group using t-test, and categorical variables will be compared using the chi-squared test. The hypotheses will be tested by logistic regression analysis to estimate the odds ratios and 95% confidence intervals for GERD control rate in the RM patients between the two arms and for the adverse events between the PM patients between the two arms. Time to-event analysis will be performed using Kaplan Meier method and a Cox regression model. Significant covariates associated with the events will be adjusted for in the multivariable models. All analysis will be performed in SAS 9.4 (Cary, NC).

We will also have a composite analysis that is conducted in the same manner that combines efficacy and safety and tests the hypothesis that genotype supported PPI dosing leads to better PPI efficacy and safety, as determined by composite of refractory GERD, and adverse effects.

Finally, we will evaluate the influence of genotype-supported dosing recommendations and will evaluate the percentage of the time when a dosing recommendation was made and accepted by the treating clinician, to provide practical data on the willingness of clinicians to adopt this approach. We will also collect patient- and provider-level survey data on attitudes about pharmacogenetics testing; using survey tools adapted from those utilized by other IGNITE groups. These will be shared for network-wide analyses, but because of the number of patients we will study, we should also have sufficient data to perform analyses on our patients along.

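### Nemours hypothesis 2 pools loss-of-function carriers whose dosing advice differs by site; at 180 patients about 56–61% are adult IMs with no recommended reduction, which can pull the estimate toward the null

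*Combined protocol and SAP*

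**What the plan says.** **Hypothesis and population.** The Nemours protocol's Statistical analysis paragraph names two primary hypotheses. The second is that "PMs (1 or 2 LOF alleles) in the genotype-supported group have fewer adverse effects" than such patients under usual care, on a composite of infections, kidney effects and fractures. The text under Table 1 of that protocol uses the same grouping, "individuals carrying a LOF allele (hereafter referred to as PMs", and leaves *2/*17 out of the primary analysis. The hypothesis sentence names no age group. Aim 2 in Specific Aims states the adverse-event hypothesis for children and adults at both sites, and the case for genotype-guided dosing under Significance repeats it for both age groups. The Study Design paragraph counts 60 children and 120 adults.

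**Dosing advice.** At Nemours (Dosing paragraph), "for participants classified as PM and IM we will recommend that their conventional (based on NM phenotype) PPI doses be reduced 50% (halved". At UF (section 7, Genotyping and result reporting), a dose increase is recommended for RMs and UMs; for the rest, "clinicians will be advised that usual PPI doses are expected to be effective that lower doses may be sufficient for symptoms management in PMs". The UF abstract separates PMs, with two LOF alleles, from "intermediate metabolizers (IM, one loss-of-function allele". An adult IM is therefore advised the usual dose.

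**Analysis.** "Significant covariates associated with the events will be adjusted for in the multivariable models". A further provision is that "In secondary analyses we will associate outcomes with the five phenotypes listed in table 1". The Nemours Power calculation gives 80% power for a 29% relative reduction, with 600 patients and 178 carriers.

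**The concern.** The hypothesis is about safety in LOF carriers, and the mechanism offered is a lower dose. If most of the analysed carriers in the genotype-supported arm receive no advice to reduce, the arm contrast mixes patients whose recommended treatment changes with patients whose recommended treatment does not. A real benefit of dose reduction in children could then appear as a small pooled effect, and a null could be misread as evidence that reduction does not help.

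The planned analyses do not deal with this. The five-phenotype analysis separates IM from PM but not by site, so child IMs (halved dose) and adult IMs (usual dose) stay together. Site enters the model only if it proves significant. Yet site carries both the dosing rule and the method of event capture: weekly interview and questionnaire at Nemours (Assessment of PPI adverse events and efficacy), medical-record review at UF (section 7).

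**Working it through.** **1. Population.** The Nemours feasibility text anticipates 350 adults and 250 children. 350 + 250 = 600, exactly the number in the Power calculation for hypothesis 2. Adults are therefore counted in that calculation.

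**2. The plan's own carrier count.** 178/600 = 29.7%. Stated frequencies do not reproduce it:
- Table 1, IM + PM: 600 × 0.217 = 130
- Table 1 with *2/*17: 600 × 0.273 = 164
- Control children in the fundoplication comparison (UF section 5, Table 4): 79 *2 carriers of 278 = 28.4%, so 600 × 79/278 = 171

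The shares below therefore use the stated frequencies, not 178.

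**3. Share of adult IMs.** Share = (adults × 0.20) / (adults × 0.217 + children × c). Here c is 0.217 (Table 1) or 0.284 (Table 4 controls, who may include some *2/*17).

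| Patients | Adult IM | Adult PM | Child LOF | Total | Share |
|---|---|---|---|---|---|
| 180, c = 0.217 | 24.0 | 2.04 | 13.02 | 39.06 | 61.4% |
| 180, c = 0.284 | 24.0 | 2.04 | 17.05 | 43.09 | 55.7% |
| 600, c = 0.217 | 70.0 | 5.95 | 54.25 | 130.2 | 53.8% |
| 600, c = 0.284 | 70.0 | 5.95 | 71.04 | 147.0 | 47.6% |

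**4. Sensitivity.** Counting *2/*17 as LOF at both sites gives 24/(180 × 0.273) = 49% and 70/(600 × 0.273) = 43%. That lowers the adult-IM share but not the dilution, because Nemours doses *2/*17 as NM and UF's usual-dose advice covers them too. Setting 70 against the plan's 178 gives 39%, but this combines two inconsistent frequencies.

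**5. Dilution.** Assume equal baseline risk, full uptake where a reduction is recommended, and no effect in adult IMs. The pooled reduction is then 0.29 × (share of carriers who benefit). The low end counts children only; the high end adds UF PMs, for whom a lower dose is optional.
- 180, Table 1: 0.29 × 13.02/39.06 = 9.7%, to 0.29 × 15.06/39.06 = 11.2%
- 180, Table 4: 0.29 × 17.05/43.09 = 11.5%, to 0.29 × 19.09/43.09 = 12.8%
- 600, the same steps: 12.1–13.4% (Table 1) and 14.0–15.2% (Table 4)

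**6. Power.** The plan states no control event rate. With two proportions, two-sided alpha 0.05 and a normal approximation, 89 per arm and a 29% reduction reach 80% at a control rate of about 0.70. This rate is back-solved, so it is an assumption. At 180 patients there are 39.06/2 = 19.5 to 43.09/2 = 21.5 carriers per arm:
- Undiluted 29% reduction: about 25–27%; at an assumed control rate of 0.40, about 11–12%
- Diluted as in step 5, control rate 0.70: about 7–9%

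**7. Precision in the Nemours carriers.** The 13–17 children give 6.5–8.5 per arm. The 95% confidence interval for a risk difference then has a half-width of about 45–52 percentage points.

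**The case against.** The strongest reply is that this is a disclosed feature of a pragmatic trial. The Nemours Dosing paragraph says the UF committee may change the adult recommendations, the Nemours safety text says no clinician action is required, and UF leaves prescribing to the physician. The overview sets out to "determine the feasibility of genetic testing in a pediatric and adult setting". On that view the by-arm contrast estimates exactly what was delivered. This stands: the pooled estimate is not biased for the strategy as delivered, and the difference in advice is not itself an error.

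A second reply is that dilution is not the main problem. This also stands. At 180 patients a null would be uninformative even under identical dosing rules, as the undiluted power shows.

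Third, the UF text is only a summary. The quick reference guides given to clinicians are not reproduced and may say more about IMs. That is a fair limit on certainty, though the summary is the only adult rule the documents give.

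Two stronger readings are tempting. A reader of the Statistical analysis paragraph alone might infer that adult inclusion is undecided, especially since UF runs under its own protocol and calls its adverse-event work exploratory. The aims, the enrolment count and the 600-patient total do not support that. A reader might also infer that results split by dosing rule would show whether halving works. They would not, because site, age, dosing rule and event capture all coincide, and the child group is too small.

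**Conclusion.** The point holds, and it is minor. Hypothesis 2 covers children and adults but pools LOF carriers under two dosing rules. With *2/*17 excluded, adult IMs with no recommended reduction make up about 56–61% of carriers at 180 patients and 48–54% at 600 (about 49% and 43% if *2/*17 is counted as LOF). If they show no effect, a 29% reduction becomes about 10–13% at 180 and 12–15% at 600. These sizes rest on the stated genotype frequencies, equal genotype mix by arm, no dropout, full uptake in children, equal baseline risk and the UF advice as summarised. The pull toward the null needs only that adult IMs benefit less than carriers advised to reduce.

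The pooled comparison answers whether the strategy as delivered reduces adverse effects. It does not answer whether dose reduction does, so a null is not evidence against reduction. The plan's 80% power does not apply to the 180 patients now planned, and that shortfall limits interpretation more than the dilution does.

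**What to change.** In the Nemours Statistical analysis and Power calculation paragraphs:

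1. Keep the by-arm comparison in all LOF carriers, described as the effect of the strategy as delivered. Prespecify site as a covariate instead of leaving it to selection by significance, because dosing rule and event capture differ by site.
2. State that the 80% power refers to 600 patients, not to 180, and label hypothesis 2 exploratory at 180. This agrees with UF section 7, which already treats adverse effects as preliminary.
3. Optionally, list the arm effect with its 95% confidence interval for Nemours PM/IM and for UF IM. Present it as description only, and note that site, age, dosing rule and event capture cannot be separated.

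The cost is a few sentences and one label. Genotype is fixed at baseline and obtained in both arms, so arm comparisons within each group remain randomised and no new data are needed. The gain is in interpretation, not power. Whether the sites should align their IM advice is a clinical decision outside this change.

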Power calculation. Briefly, with 600 participants in the trial, we will have 80% power at alpha level of 0.05 to detect a relative risk of 1.35 or higher in the GERD control within RM patients in the usual care vs. the genotype-supported arm. This assumes that among the 600 participants, 33% will have the RM phenotype, and half will be randomized to each arm of the study. For the adverse event hypothesis, with 600 patients, we expect to have 178 PM patients, with 89 patients in each arm. At alpha level of 0.05, we will have 80% power to detect relative risk reduction of 29% or more in the adverse events for PM patients in the genotype supported group compared to those in the usual care group.

Clinical Trials.gov. This trial requires registration in ClinicalTrials.gov.

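### Nemours primary hypotheses: the power targets are relative risks but the planned estimates are odds ratios, with no risk ratio or risk difference, and the 1.35 target runs opposite to hypothesis 1

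*Combined protocol and SAP*

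**What the plan says.** In the Nemours part of the document (study design for Aim 2), the statistical analysis paragraph names two primary hypotheses. Hypothesis 1 is that RMs have better GERD control in the genotype-supported arm than in usual care. Hypothesis 2 is that PMs have fewer adverse effects in the genotype-supported arm. The analysis is: "The hypotheses will be tested by logistic regression analysis to estimate the odds ratios and 95% confidence intervals for GERD control rate", and the same sentence covers adverse events in PMs. Kaplan-Meier and Cox analyses are added, and covariates found significant are to enter multivariable models. No risk ratio or risk difference is mentioned.

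The power paragraph uses another scale. For GERD control the trial is sized "to detect a relative risk of 1.35 or higher in the GERD control within RM patients in the usual care vs. the genotype-supported arm". It assumes 600 participants, of whom "33% will have the RM phenotype, and half will be randomized to each arm of the study". For adverse events it says "with 600 patients, we expect to have 178 PM patients, with 89 patients in each arm", and claims "80% power to detect relative risk reduction of 29% or more in the adverse events for PM patients". It gives no usual-care rate for either outcome and does not say whether alpha is one- or two-sided.

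**The concern.** An odds ratio is close to a relative risk only when the outcome is rare. When it is common, the odds ratio lies further from 1, by an amount that depends on the reference rate. The plan gives no such rate, so an odds ratio from the primary model cannot be placed against 1.35 or 0.71.

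Covariate adjustment widens the gap. An odds ratio is non-collapsible: even without confounding, the adjusted value differs from the marginal one and changes with the covariates chosen. A reader cannot simply convert it to the planned relative risk.

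The direction of the first target is a separate fault. A ratio of 1.35 or more "in the GERD control within RM patients in the usual care vs. the genotype-supported arm", taken literally, means that usual care controls GERD better. Hypothesis 1 says the opposite.

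At stake is whether the reported effects can be compared with what the trial was designed to detect, and whether they are read at their true size.

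**Working it through.** **Inputs.** All come from the Nemours power paragraph: alpha 0.05; power 80%; adverse events, 89 per arm, relative risk 1 − 0.29 = 0.71; GERD control, 0.33 × 600 = 198 RMs, so 99 per arm, relative risk 1.35.

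**Reproducing the 80%.** This cannot be done forwards, because the reference rate is missing. I therefore solved for the rate that gives exactly 80%, assuming a two-sided test and the usual two-proportion formula with pooled null variance:

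power = Φ( [ |p₁ − p₂|·√n − 1.96·√(2p̄(1 − p̄)) ] / √(p₁(1 − p₁) + p₂(1 − p₂)) )

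with p₁ the usual-care rate, p₂ = RR × p₁ and p̄ their mean. Then OR = [p₂/(1 − p₂)] / [p₁/(1 − p₁)].

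- Adverse events: p₁ = 0.704, p₂ = 0.500. Numerator 0.204 × 9.434 − 1.96 × 0.692 = 0.568; denominator 0.677; ratio 0.84; power 80%. OR = 1.00 / (0.704/0.296) = 0.42.
- GERD control, with the ratio turned to match hypothesis 1: p₁ = 0.543, p₂ = 0.734. The same steps give 80%, and OR = 2.31.

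**Sensitivity to the test assumed** (unpooled variance, continuity correction, arcsine, Wald test on the log odds ratio):

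| | Adverse events: usual-care rate | Adverse events: OR | GERD control: OR |
|---|---|---|---|
| Two-sided variants | 70% to 73% | 0.39 to 0.43 | 2.28 to 2.46 |
| One-sided variants | 63% to 67% | 0.45 to 0.48 | 2.04 to 2.17 |

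**Sensitivity to the adverse-event rate**, holding the relative risk at 0.71 (power is for 89 per arm, two-sided, pooled):

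| Usual-care rate | OR | Power |
|---|---|---|
| 20% | 0.66 | 17% |
| 40% | 0.60 | 37% |
| 50% | 0.55 | 50% |
| 60% | 0.50 | 64% |
| 70% | 0.42 | 79% |
| 80% | 0.33 | 92% |

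The odds ratio is further from 1 than the relative risk at every rate. The gap is modest at 20%, but the claimed 80% power is not available there: that claim itself needs a common outcome.

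**Does the scale change the test?** Hardly. With a Wald test on the log odds ratio, 80% power at 89 per arm needs 71.3% versus 50.6% (OR 0.41), almost the same design point.

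**Numbers actually planned.** The Nemours study design paragraph enrols 180 (60 children, 120 adults), not 600. At 33% RM that is 180 × 0.33 / 2 ≈ 30 per arm. With Table 1's frequencies for one or two loss-of-function alleles (20% + 1.7% = 21.7%), it is 180 × 0.217 / 2 ≈ 20 PMs per arm.

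**The case against.** **The 0.42 is not in the plan.** This stands. It rests on a back-solved rate near 70% and a two-sided test, neither of which is stated. It also uses 89 per arm from the 600-participant text. Moreover, 178 PMs is 29.7% of 600, whereas Table 1 gives 21.7%, or about 130. With 65 per arm the same back-solve gives 79% versus 56% and an odds ratio of 0.34. So 0.42 is an implied figure. A reader might infer that a true 29% reduction will be reported as 0.42; the documents do not support that as a fact.

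**Other outputs are planned.** The plan includes chi-squared tests and Cox models, and the adverse-event assessment compares symptom prevalence between arms. If proportions by arm are reported for the RM and PM subgroups, a crude risk ratio can be worked out. That is fair, but no such estimate or interval is specified for either primary hypothesis. It would not match an adjusted model, and a hazard ratio is a third scale.

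**The targets could be restated as odds ratios.** That would align the scales too. However, the adjusted odds ratio depends on covariates chosen by significance, so a fixed odds-ratio target would still be awkward to compare with it.

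**The direction is a drafting slip.** Probably so. Hypothesis 1 is clear, and with equal arms and a two-sided test, swapping the labels leaves power unchanged. It does not follow that the trial was sized for the wrong hypothesis. The phrase still needs correcting.

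**Two tempting extensions fail.** The background statement that PPI treatment fails in up to 40% might suggest a planned control rate of 60%. It is an upper bound across genotypes and is not cited in the power text. At 60% the power would be about 91%, not the stated 80%. A reader might also expect the odds ratio to under-size a later trial. The language about informing a later study is in the UF protocol, and it concerns adverse-event incidence and power inputs, not this odds ratio.

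**Conclusion.** The point holds as one of estimation and interpretation. Both Nemours targets are relative risks, both primary models give odds ratios, possibly covariate-adjusted, and nothing planned puts the estimates on the scale of the targets. The 1.35 is also written against the direction of hypothesis 1. Both mismatches are plain in the text and need no assumption.

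The size of the gap does rest on assumptions. Under a two-sided pooled test, the plan's own sample sizes, relative risks and 80% power imply odds ratios of about 0.42 and 2.3. If the adverse-event rate is left open from 20% to 80%, the odds ratio matching a relative risk of 0.71 runs from 0.66 to 0.33.

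A reader might infer that the logistic analysis is invalid or loses power; it is a sound test of both hypotheses. The conflict between 600 and 180 participants does undermine the stated 80%, but that is a separate problem in the same paragraph. It neither causes nor removes the mismatch of scales.

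**What to change.** **Statistical analysis paragraph.** Keep logistic regression as the test. Beside the odds ratio, report the marginal risk ratio and risk difference with 95% confidence intervals, standardised from the same fitted model: predict each patient's risk under each arm, average, and contrast. With only about 20 PMs and 30 RMs per arm at 180 patients, use bootstrap or small-sample-corrected intervals and name the method in advance.

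**Power paragraph.** Write the GERD-control ratio as genotype-supported versus usual care. State the assumed usual-care rates for both outcomes and the sidedness of alpha. Reconcile the 600-participant basis, and the 178 PMs derived from it, with the 180 in the study design paragraph.

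**Cost.** A few sentences of plan text and modest extra SAS programming; no new data or visits. The drawbacks are slightly more analysis work and an effect size that looks less striking than the odds ratio.
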